12.4 Analysis of secondary endpoints

SARS-CoV2 Log₁₀ viral loads at follow-up timepoints will be compared between groups using the Wilcoxon rank-sum test and/or generalized estimating equations with robust standard errors. The area-under-the-curve (AUC) SARS-CoV2 viral RNA levels during follow-up will be estimated using the linear trapezoidal method, and mean AUC levels compared between groups using the Wilcoxon rank-sum test.

The distribution of cessation of symptoms will be estimated using the Kaplan-Meier method, and Kaplan-Meier curves will be presented for each treatment arm. Time to cessation of symptoms at the end of the study period along with 95% confidence intervals will be presented for each treatment arm. The hazard ratio for cessation of symptoms will be estimated, along with its 95% confidence intervals, from a Cox proportional hazards model. Time to cessation of symptoms will be estimated in the subgroup of patients who are symptomatic at baseline.

The incidence of hospitalizations and emergency department visits will be compared between groups using negative binomial regression models, which will account for differing follow-up times through an offset term.

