### 1.3 Secondary endpoints

Secondary endpoints include the following:

- Time until resolution of all symptoms;
- SARS-CoV-2 viral load over time in oropharyngeal tests;
- SARS-CoV-2 viral load area under the curve in oropharyngeal tests through Day 14;
- Number of emergency department visits or hospitalizations within 28 days of treatment.

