## 2.2 Descriptive analyses

Descriptive statistics (proportions for categorical variables, means, medians, standard deviations and interquartile ranges for continuous variables) will be reported for all key patient variables, including baseline and demographic characteristics, use of medications, compliance, and study completion status. Data that are missing on key patient characteristics and the outcome will be fully described, including any patterns of missingness (i.e., any relationships between missingness of a variable and patient characteristics).

A CONSORT diagram displaying the number of patients screened, eligible, and consented along with reasons for ineligibility will be provided. Graphical tools such as histograms, boxplots, and scatterplots will be created to assess quality of data and to display patterns over time.

All tests will be performed at the alpha = 0.05 level of significance unless otherwise noted.

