### **2.4 Secondary efficacy analyses**

Time to resolution of all symptoms will be defined as the time from randomization until the first study day in which no symptoms are reported. The distribution of time to resolution of symptoms will be estimated using the Kaplan-Meier method, and Kaplan-Meier curves will be presented for each treatment arm. Time to symptom resolution at the end of the study period along with 95% confidence intervals will be presented for each treatment arm. The hazard ratio for resolution of symptoms will be estimated, along with its 95% confidence intervals, from a Cox proportional hazards model adjusted for age and sex.

We will model SARS-CoV-2 viral load in oropharyngeal tests over time using a generalized mixed effects linear regression model with a random effect for study participant to account for correlation within a participant. Viral load with cycle threshold (Ct) values above the limit of detection will be calculated by substituting a Ct value of 42 into the equation  $10^{(Ct - 42) * 0.23}$  to derive viral load from Ct. A logarithmic transformation on viral load will be fit to treatment arm, time, armXtime, and adjusted for age and sex to account for therandomization stratification variables. The armXtime interaction term will allow us to assess whether the trajectory of viral load differs by treatment arm. Time will be defined as days from randomization and, depending on model fit, will either be modeled continuously or with a flexible approach allowing a non-linear trajectory for the change in viral load over time. Model fit will be assessed based on visual inspection of the residuals. Alternative transformations or generalized linear models with a link function besides the identity link will be considered if the model does not fit the data well.

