Area under the curve (AUC) will be defined by a single participant's logarithmic base 10 viral load from oropharyngeal tests collected on days 0, 1, 3, 5, 7, 10, and 14. AUC will be calculated by the trapezoidal rule, using exact times of collection of each OP swab. Multiple imputation using chained equations will be used to impute missing viral load data prior to AUC calculation. Five data sets will be imputed, and imputed values will be calculated using non-missing viral load on each of the 7 sample collection days, treatment arm, age, sex, and whether or not a participant was hospitalized. A pooled linear regression model will be fit to log-transformed AUC as a function of treatment, age, and sex using the 5 imputed data sets. Difference in AUC by treatment arm and corresponding 95% confidence intervals will be reported using Rubin's Rules. The difference in AUC by treatment arm will also be done after refitting the model without participants who were hospitalized to assess sensitivity of results.

The incidence of hospitalizations and emergency department visits will be estimated for each arm, with 95% confidence intervals.

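### The viral-load arm-by-time test in SAP 2.4 relies on one participant random effect and no robust errors, so it may not hold its 5% level

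*SAP*

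**What the plan says.** SAP 1.3 lists "SARS-CoV-2 viral load over time in oropharyngeal tests" as a secondary endpoint. SAP 2.4 regresses log viral load on arm, time, arm by time, age and sex, "with a random effect for study participant to account for correlation within a participant". The interaction carries the treatment question: "The armXtime interaction term will allow us to assess whether the trajectory of viral load differs by treatment arm". Undetectable values go to a floor: "Viral load with cycle threshold (Ct) values above the limit of detection will be calculated by substituting a Ct value of 42". Time is measured in days from randomization and, "depending on model fit, will either be modeled continuously or with a flexible approach allowing a non-linear trajectory". Fit is judged by looking at residuals, and the alternatives offered are other transformations or link functions.

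SAP 2.2 sets the level: "All tests will be performed at the alpha = 0.05 level of significance unless otherwise noted". No end day is given for this model. The AUC in the same section uses swabs "collected on days 0, 1, 3, 5, 7, 10, and 14", while clinic visits run to day 28 (Protocol 9.1.2). For the same endpoint, Protocol 12.4 lists the Wilcoxon test and, as an alternative or addition, "generalized estimating equations with robust standard errors". SAP 2.5 uses similar methods for nasal swabs.

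**The concern.** A random intercept lets participants differ in level only. It assumes that everyone in an arm shares one trajectory shape and that residuals around it are independent. SAP 4.2 assumes shedding of 14 days on average with SD 4, so participants reach the Ct 42 floor on different days and their trajectories differ in shape. Arm by time is a contrast of slopes. Its true standard error depends on how much slopes vary between participants, and the random-intercept standard error accounts for that variation only in part, through the residual variance. None of the listed fallbacks changes the covariance, and the SAP 3 sensitivity analyses concern missing data.

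At stake are the p-value and confidence interval of the planned test of whether Lambda changes the viral-load course, and the same quantities for the exploratory nasal analysis.

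**Working it through.** **Inputs from the documents.** 60 per arm (SAP 1.1); 5% level, taken as two-sided (SAP 2.2); swab days 0, 1, 3, 5, 7, 10, 14, plus 21 and 28 (SAP 2.4, Protocol 9.1.2); duration 14 days, SD 4 (SAP 4.2); about 10^6 copies at diagnosis (Protocol 2.1.1); floor at Ct 42.

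**Assumed, because the documents are silent.** Swab noise SD 2, 4 or 6 Ct (times 0.23: 0.46, 0.92 or 1.38 log10); detection limit Ct 40; starting Ct 16, 24 or 28; lognormal slopes. The sign of the Ct-to-load conversion does not affect null rejection.

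**1. Closed form, linear time, no floor.** Let n be participants per arm, m the number of visits, S the sum of squared deviations of visit days, σ the residual SD and τ the SD of slopes between participants.

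- True variance of arm by time: (2/n)(τ² + σ²/S)
- Random-intercept model variance: (2/n)(σ² + τ²S/(m−1))/S
- Actual level: 2[1 − Φ(1.96 × √(model/true))]

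To day 14, S = 380 − 40²/7 = 151.4 with m − 1 = 6. To day 28, S = 1605 − 89²/9 = 724.9 with m − 1 = 8.

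The plan's 5% is reproduced when τ = 0: the two variances are equal and the level is 0.050 (simulation 0.051).

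With σ = 1 log10 (assumed) and τ = 0.10 log10/day, to day 14:

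- true: 0.0100 + 0.0066 = 0.0166
- model: (1 + 0.01 × 151.4/6)/151.4 = 0.0083
- √(0.0083/0.0166) = 0.706, and 1.96 × 0.706 = 1.38, so the level is 0.167

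| τ (log10/day) | to day 14 | to day 28 |
|---|---|---|
| 0 | 0.050 | 0.050 |
| 0.05 | 0.085 | 0.196 |
| 0.10 | 0.167 | 0.346 |
| 0.15 | 0.242 | 0.412 |

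As a rough guide to τ: if everyone started at 10^6 copies and all spread in duration came from slope, τ ≈ 6 × 4/14² = 0.12. It is smaller if part of the spread comes from starting level. The table ignores the floor, so it shows the mechanism and is not a prediction.

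**2. With the floor, linear time.** Ct = start + slope × day + noise, with values above the limit set to 42. Starting and slope spread are solved to give 14 ± 4 days to the floor, with the spread coming from start, slope or half each. There are 27 settings with 4,000 null trials each.

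- To day 14: 4-18% (6-18%, 4-10% and 4-6% at noise 2, 4 and 6 Ct). The ratio of true to model SE is 0.94-1.45. Check: 1.96/1.45 = 1.35 gives 18%; 1.96/0.94 = 2.09 gives 4%.
- To day 28: 0-22%. The SE ratio is 0.37-1.60. Check: 1.96/1.60 = 1.23 gives 22%; 1.96/0.37 = 5.3 gives about 0.

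The test can become conservative to day 28 because a straight line misses the plateau, and that misfit enlarges the model's residual variance.

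**3. Sensitivity to the assumptions.** Detection limits of Ct 38 or 42 give 3-23% to day 14 and 0-24% to day 28. Exponential clearance times with median 14 days give 7-22% and 4-21%. A separate set-up on the log10 scale (start 6, SD 1; floor at 0) gives 20%, 11% and 8% to day 14 at residual SD 0.5, 1.0 and 1.5, and 3-4% to day 28.

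**4. Flexible time, still with a random intercept.** Under the assumptions of step 2, visit categories give 5-8% to day 14 and 6-13% to day 28. Quadratic or cubic time gives about 3-19% and 3-30%.

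**5. Clustering by participant.** A two-sample t test on participant slopes rejects 4-6% under the assumptions of step 2 and with exponential clearance. Fitted REML random-intercept models were also run with age, sex, ±1-day visits and 10% dropout (start Ct 24, 18 settings, 1,000 trials each). Model-based tests reject 2.7-14.9% to day 14 and 0-22.3% to day 28; participant-clustered robust tests reject 3.7-6.1%. With spread half each, days 0-14 and noise 2, 4 and 6 Ct, the figures are 11.8%, 7.1% and 4.5% model-based against 4.9%, 5.8% and 5.2% robust.

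**6. Why a small-sample correction.** With slopes varying freely or the log10 floor set-up, uncorrected clustered tests reject 5.0-6.3% with dropout, a slight excess. For a 6-df test in 120 participants, the uncorrected chi-square cut-off 12.59 corresponds to F(6,113) = 12.59 × 113/(6 × 118) = 2.01, which is exceeded 7.0% of the time.

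**The case against.** The strongest reply is that SAP 2.4 is brief, not wrong. It says a random effect, does not rule out a slope or robust errors, and leaves other choices to model fit. That supports saying the test may not hold its level as written; it does not support saying that it fails. An edit is needed either way, because a random slope, if intended, is not stated.

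The size also rests on variances the documents do not give. With linear time to day 14, 14 of 27 settings reject at 6.0% or less, and all settings above 10% use the lowest noise, 2 Ct. The 14 ± 4 days is read here as time from randomization to the floor in outpatients. SAP 4.2 does not say so, and its source is by title an inpatient cohort. All of this stands, and it is why only a range is given.

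Three stronger readings are tempting and are not supported:

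- **That the level is inflated.** To day 28 the linear test can be conservative, so the error can go either way.
- **That a straight line could make the arm that clears sooner look slower.** This needs a line kept despite visible curvature, and SAP 2.4 provides a non-linear form and residual checks.
- **That the SAP breaks a Protocol commitment.** Protocol 12.4 offers robust errors as one option beside the Wilcoxon test. Plain GEE would also fit poorly with the missing-at-random assumption in SAP 3.

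**Conclusion.** The concern holds in limited form. As written, the arm-by-time test takes its standard error from a covariance that the SAP's own planning figures make doubtful, and nothing else in the plan repairs it. Under 14 ± 4 days to the floor, the true level is roughly 4-18% with linear time to day 14, near 5% when swab noise is high, and 0-22% to day 28. These are ranges under assumed noise, detection limit and starting levels; they do not predict this trial's error. A flexible time form is not a dependable cure.

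The consequence is confined to one secondary endpoint and its exploratory nasal counterpart. A reader might infer that the efficacy conclusion is at risk, but the primary Cox analysis does not use this model, and the AUC analysis reduces each participant to one value. The change is worth making because it costs very little.

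**What to change.** In SAP 2.4, keep the mixed model and time as days from randomization, and add:

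- Arm by time is reported, as the main result, with participant-clustered robust standard errors and a small-sample correction (an F reference if the interaction has several degrees of freedom). A random slope may be added.
- The analysis window is stated, for example days 0-14 to match the AUC.
- The same clustered errors apply to the nasal analysis in SAP 2.5.

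Suggested text: *Arm by time over Days 0-14 will be tested in the mixed model using standard errors clustered by participant, with a small-sample correction. The random-effects structure and the form of time will be stated with the result.*

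Protocol 12.4 should be aligned. Robust errors on the mixed model stay closer to the SAP 3 missing-data assumption than a switch to plain GEE.

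The cost is wording and one model option, with no new data. Intervals will usually be slightly wider, and days 21 and 28 become descriptive if the window ends at day 14.

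Visit categories with unstructured covariance and an F test are an optional alternative. They can lose power against a single slope contrast, and they do not suit daily nasal swabs: 15 days need 15 × 16/2 = 120 covariance parameters for 120 participants.

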6.2 Inclusion Criteria

Patients must fulfill all of the following inclusion criteria to be eligible for the study:

1. Age \geq 18 years and \leq 75 years at the time of the assessment
2. Able and willing to understand the study, adhere to all study procedures, and provide written informed consent
3. Diagnosis of COVID-19 disease:
 - a. If symptomatic, presence of mild to moderate symptoms without signs of respiratory distress, with FDA-cleared molecular diagnostic assay positive for SARS-CoV-2 within 72 hours from swab to the time of commencing informed consent:
 - b. If asymptomatic, initial diagnosis of SARS-CoV-2 infection with positive FDA-cleared molecular diagnostic assay obtained no more than 72 hours from initial swab to the time of commencing informed consent

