9.3 Virologic assessments

Oropharyngeal and anterior nare swabs for SARS-CoV2 RNA will be collected using a standardized technique at all study visits. Additionally, participants will be instructed in collection of anterior nasal swabs at home and asked to collect a swab each day. We will ask participants to collect stool at home (between days 0-3, 10-14, and 21-28; and at 4, 7 and 10 months post-randomization). All swabs will be collected in viral transport media or phosphate buffered saline. Stool will be collected in stabilization tubes, kept at room temperature, and brought to the next study visit. Samples collected in the clinic will be refrigerated and transported the same day to the Stanford clinical virology laboratory for processing. We will ask that swabs collected at home be stored in a 4 degree refrigerator until their study visit, at which point they will be transferred to the study team and transported to the clinical virology laboratory. Fridges will be provided to the participants at enrolment. In the clinical virology laboratory, samples will undergo automated nucleic acid extraction followed by a FDA-cleared quantitative real-time PCR assay for SARS-CoV-2, which will generate both qualitative (positive or negative) and quantitative (estimated viral copies) results. The assay is validated for nasopharyngeal, oropharyngeal, and anterior nare samples. The stool assays have been analytically validated and are undergoing clinical validation.

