## 2.5 Exploratory efficacy analyses

An alternative definition of the secondary endpoint of symptom resolution will be considered in an exploratory analysis. We will evaluate time to sustained symptom resolution, defined as time from randomization until the first day in which no symptoms are reported and are not reported for the duration of the study. The analysis of time to sustained symptom resolution will follow the methods described for the secondary endpoint evaluation symptom resolution in the previous section. Time to symptom resolution based on symptom subsets (i.e. respiratory, systemic) will be similarly analyzed, additionally excluding participants who did not report symptoms from the specified subset at screening.

Time to disease progression will be defined as the time from randomization until the first day of a two point or more increase in either cough or shortness of breath persisting for at least 48 hours or an increase to a score of 4 or 5, or first day of admission to the emergency department, hospitalization, or death. Analysis and reporting of results will be done following methods detailed for time to symptom resolution.

Freedom from SARS-CoV-2 infection by oropharyngeal and nasal swabs at Day 5, 7, 10, and 14 will be modeled using a multivariable logistic regression model adjusted for age and sex. The odds ratio will be presented along with its 95% confidence interval.

Similar approaches to those used for evaluating SARS-CoV-2 viral load in oropharyngeal tests over time and AUC will be used to evaluate viral load in nasal tests.

Correlation between virology and symptomology will be characterized by evaluating the relationship between CT values obtained from the oropharyngeal tests and each symptom through two main approaches. For symptoms graded on an ordinal scale, we will calculate a Spearman correlation and assess significance with a Z-test. For variables that capture presence of a symptom, differences in the median CT values by presence or absence of the symptom will be presented and assessed via a Wilcoxon rank sum test.

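### SAP 2.4 fits a linear model to the log of an AUC that is already built on log10 viral load, with no rule for AUC = 0; the sign of the Ct equation also needs checking against the source page

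*SAP*

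**What the plan says.** SAP 2.4 defines the secondary AUC endpoint from each participant's "logarithmic base 10 viral load from oropharyngeal tests collected on days 0, 1, 3, 5, 7, 10, and 14", by the trapezoidal rule, after multiple imputation of missing loads. It then states: "A pooled linear regression model will be fit to log-transformed AUC as a function of treatment, age, and sex". It gives no offset and no rule for an AUC of zero. The allowance in SAP 2.4 for other transformations belongs to the model of viral load over time, not to the AUC model.

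For swabs past the detection limit, SAP 2.4 says that viral load "will be calculated by substituting a Ct value of 42 into the equation" 10^((Ct − 42) × 0.23), which it describes as the equation "to derive viral load from Ct". SAP 2.5 extends the methods to the nose: similar approaches to those for load over time and "AUC will be used to evaluate viral load in nasal tests".

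Protocol 12.4 has "mean AUC levels compared between groups using the Wilcoxon rank-sum test". Protocol 9.3 describes an assay "which will generate both qualitative (positive or negative) and quantitative (estimated viral copies) results".

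**The concern.** A log of AUC is a usual choice when the AUC is on the copies scale. Here the AUC is already on the log10 scale, where an undetected swab scores exactly 0. A second log fails at AUC = 0 and stretches the region just above it. The participants at that end carry least virus, and for an antiviral they matter most. Dropping them would also conflict with SAP 2.1, which puts all efficacy analyses in the ITT population, and the dropping would depend partly on swabs taken after treatment. Multiple imputation does not help, because an AUC of 0 is observed, not missing.

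The equation raises a second, conditional question. Its exponent increases with Ct, although the same sentence treats high Ct as undetected.

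At stake are two of the four secondary endpoints in SAP 1.3 (the second log touches only the AUC) and the matching nasal analyses.

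**Working it through.** The plan gives no figure of its own to reproduce on this point.

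**Inputs.** Visit days 0, 1, 3, 5, 7, 10 and 14, slope 0.23 and substitution value Ct 42 come from SAP 2.4. The Ct paths are my assumptions. The AUC calculation takes load as falling with Ct: log10 load = 0.23 × (42 − Ct).

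**Zero AUC.** At Ct 42, log10 load = 0.23 × 0 = 0. Seven zeros give AUC = 0, and log(0) is undefined. This holds under either sign of the exponent. It also holds if detected swabs use the assay's own copies, because undetected swabs still score 0.

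**Can it occur?** Protocol 6.2 requires, for symptomatic patients, an "FDA-cleared molecular diagnostic assay positive for SARS-CoV-2 within 72 hours from swab to the time of commencing informed consent", with the same 72-hour limit for asymptomatic patients. It does not require a positive oropharyngeal swab on day 0. So it can occur.

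**Near-zero AUC.** For the slow clearer (Ct 24, 25, 27, 30, 33, 37, 42), the trapezoids of 42 − Ct are 17.5 + 32 + 27 + 21 + 21 + 10 = 128.5, and × 0.23 = 29.56. For the fast clearer (Ct 24, 26, 30, 34, 38, 42, 42), they are 17 + 28 + 20 + 12 + 6 + 0 = 83, and × 0.23 = 19.09. One detected day 0 swab followed by none gives AUC = 0.23 × (42 − Ct) ÷ 2.

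| Path | AUC | log10(AUC) |
|---|---|---|
| Slow clearer | 29.56 | 1.471 |
| Fast clearer | 19.09 | 1.281 |
| One swab, Ct 24 | 2.07 | 0.316 |
| One swab, Ct 30 | 1.38 | 0.140 |
| One swab, Ct 40 | 0.23 | −0.638 |
| One swab, Ct 41 | 0.115 | −0.939 |
| None detected | 0 | undefined |

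The slow-fast gap is 0.190 with the second log and 10.47 without it. The gap from the fast clearer to the one-swab participant, as a multiple of the slow-fast gap, is:

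| Day 0 Ct | With second log | Without |
|---|---|---|
| 24 | 0.965 ÷ 0.190 = 5.1 | 17.02 ÷ 10.47 = 1.6 |
| 30 | 1.141 ÷ 0.190 = 6.0 | 17.71 ÷ 10.47 = 1.7 |
| 40 | 1.919 ÷ 0.190 = 10.1 | 18.86 ÷ 10.47 = 1.8 |
| 41 | 2.220 ÷ 0.190 = 11.7 | 18.98 ÷ 10.47 = 1.8 |

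These multiples do not depend on the base of the second log.

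**Sign of the equation.** As the exponent reads, log10 load = 0.23 × (Ct − 42): −5.06 at Ct 20, −2.76 at Ct 30, −0.46 at Ct 40 and 0 at Ct 42. An undetected swab then has the highest load. Protocol 2.1.1 cites a median of 10^6 oropharyngeal copies at diagnosis. As the exponent reads, that needs Ct = 42 + 6 ÷ 0.23 = 68.1, well past the substitution value. With the sign reversed it needs 42 − 6 ÷ 0.23 = 15.9. The two versions of log10 load are exact mirror images. If detected swabs pass through the equation as it reads, the arm, time and arm-by-time coefficients change sign with the same p-values, and every AUC is zero or negative (slow clearer −29.56, fast clearer −19.09).

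**The case against.** On the second log, the phrase may be loose wording for the AUC of log10 load. SAP 2.4 goes on to report a difference in AUC, which fits an AUC left on that scale. That stands as a possible reading. It does not remove the need to edit, because a programmer who follows the sentence as written would take the second log.

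The Wilcoxon test in Protocol 12.4 handles AUC = 0 without a log or an exclusion. That is real but partial relief, since the SAP regression still has no rule.

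Zero AUCs may also be uncommon. The background cited in Protocol 2.1.1 has all patients shedding in the oropharynx 7 days after symptom onset. Against that, asymptomatic patients are eligible, and SAP 2.7 plans an analysis by baseline antibody status, so later presenters are foreseen. The documents settle the frequency neither way. A reader might infer that the AUC analysis is bound to fail or to lose many participants; the documents do not show that.

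On the sign, a reader might infer that the trial would report viral-load effects in the wrong direction. The documents do not support that. The evidence is one exponent read from PDF by a program, where a minus sign can be lost, and no other place prints the equation. The SAP also does not say that detected swabs use the equation. If they use the assay's copies, only Ct 42 enters it, the result is 1 under either sign, and nothing reverses. The plots over time in SAP 2.2 would probably expose a reversal in any case.

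**Conclusion.** The point holds for the AUC model. As written, SAP 2.4 takes the log of an AUC of logs, leaves AUC = 0 without a value, and turns participants with little virus into outliers. The size, about 5 to 12 times the slow-fast gap against 1.6 to 1.8 times without the second log, rests on assumed Ct paths and on load falling with Ct at 0.23 log10 per cycle. The number of participants affected is unknown.

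The sign is a conditional, secondary point. It matters only if the source prints the exponent as it reads here and detected swabs go through the equation.

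Both points concern secondary and exploratory viral-load analyses. The primary endpoint uses positive or negative results, and the analyses of raw Ct in SAP 2.5 and 2.7 do not use the equation, so neither is affected. This should be fixed before the analysis, but it does not threaten the main conclusion.

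**What to change.** 1. In SAP 2.4, model the AUC of log10 viral load directly and delete *log-transformed* before AUC. If a second log is truly intended, state the rule for AUC = 0. Apply the same to the nasal AUC in SAP 2.5. This is needed whatever the check of the sign shows.
2. Check the exponent against the source page. If it is printed as it reads here, change it to 10^((42 − Ct) × 0.23), after confirming it against the laboratory's calibration, which the documents do not give.
3. Add a sentence saying whether detected swabs use this equation or the assay's estimated copies.

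The cost is one deleted phrase, one sentence, at most one corrected exponent, and the matching program lines. No new data are needed. Done before unblinding, it avoids choosing a transformation or a zero rule after the results are seen.

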## 2.7 Effect modification, subgroup, and sensitivity analyses

A subgroup analysis will be performed for the primary endpoint using only patients who present with symptoms at baseline.

A statistical interaction term between treatment arm and the following baseline characteristics will be added to the Cox proportional hazards model to test for effect modification.

- 1) CT value < 30 from the baseline OP swab,
- 2) presence of antibodies as defined by presence of IgG antibodies to SARS-CoV-2 Spike Receptor Binding Domain (RBD) at baseline, as measured by ELISA. Samples are considered seropositive against RBD if their absorbance value was greater than the mean of plus four standard deviation (SD) of all negative controls (n=130),
- 3) number of risk factors or predictors for severe disease present at baseline (temp 99.5+, cough, or shortness of breath present at randomization [symptoms count as a single risk factor], age  $\geq$  60, male sex, Black race, Hispanic ethnicity, BMI  $\geq$  30, and lab values of baseline lymphocyte counts <1000 and baseline ALT  $\geq$  94),
- 4) age  $\geq$  50,
- 5) sex

A Wald test performed at the alpha = 0.05 level of significance will be used to test whether the effect modification is statistically significant. The sensitivity and effect modification analyses will be performed in other key endpoints as well.

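### The viral-load mixed model in SAP 2.4 estimates a Day-0 arm difference that randomization already makes zero in expectation; the test stays valid, but a common Day-0 mean would make it more precise at almost no cost

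*SAP*

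**What the plan says.** SAP 1.3 lists "SARS-CoV-2 viral load over time in oropharyngeal tests" as a secondary endpoint. SAP 2.4 analyses it with a mixed model: "A logarithmic transformation on viral load will be fit to treatment arm, time, armXtime, and adjusted for age and sex", "with a random effect for study participant to account for correlation within a participant". The term of interest is the interaction: "The armXtime interaction term will allow us to assess whether the trajectory of viral load differs by treatment arm". On the time scale it says: "Time will be defined as days from randomization and, depending on model fit, will either be modeled continuously or with a flexible approach".

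A baseline swab exists. The AUC analysis in SAP 2.4 uses "oropharyngeal tests collected on days 0, 1, 3, 5, 7, 10, and 14", and SAP 2.7 uses "CT value < 30 from the baseline OP swab" as an effect modifier. Nothing in either document gives the two arms a common Day-0 mean or adjusts this model for baseline viral load. Protocol 12.4, which names rank-sum tests and/or GEE for the same endpoint, has no baseline adjustment either. SAP 2.5 carries a similar approach over to the nasal swabs.

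Two details are left open. SAP 2.4 does not say whether the Day-0 value is one of the model's responses. No readable passage says that the Day-0 swab precedes the injection; Protocol 6.6 mentions only blood collection at intake, and the schedule of events did not survive in the text reviewed.

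**The concern.** With time counted from randomization, the coefficient for arm is the arm difference at time 0, before any drug effect is possible. In a randomized trial it differs from zero only by chance. Estimating it alongside armXtime costs precision because the two estimates are negatively correlated: if one arm's Day-0 swabs happen to read high, the fitted intercept difference rises and the fitted slope difference tilts the other way through regression to the mean.

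Randomization is stratified by age and sex only, so chance imbalance in baseline viral load is not otherwise controlled. At stake is the precision of a named secondary endpoint for which the documents state no power. Leaving Day 0 out of the responses would not help: the free time-0 difference would then be extrapolated, and the baseline information lost.

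**Working it through.** **Figure to reproduce.** There is none. The only sizing in the documents (SAP 4.2: 79 events, hazard ratio 2.03, 120 patients) is for the primary time-to-event comparison.

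**Inputs from the documents.** 60 per arm (SAP 1.1). Swab days 0, 1, 3, 5, 7, 10, 14, stated for the AUC and assumed here for the mixed model; Days 21 and 28 added as a second case (visit days in Protocol 9.1.2). Participant random effect (SAP 2.4). Alpha 0.05 (SAP 2.2), taken as two-sided.

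**Assumed, because the documents give no values.** Between-person SD 1.0–1.7 and within-person SD 1.0–1.5 log10; random slope SD 0 or 0.1 per day; linear time for the main calculation.

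**Formulas.** Let V be the covariance matrix of one person's measurements, t the vector of days, 1 a vector of ones, n = 60, and

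A = t′V⁻¹t, B = 1′V⁻¹t, C = 1′V⁻¹1.

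- Planned model (arm + time + armXtime): Var = (2/n) / (A − B²/C)
- Common Day-0 mean (time + armXtime): Var = (2/n) / A
- Relative efficiency of the plan: RE = 1 − B²/(AC)

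**One case by hand.** Between-person and within-person SD both 1.0 give an intraclass correlation (ICC) of 0.5. Scale the total variance to 1. With seven visits, Σt = 40 and Σt² = 380, and V⁻¹ = 2(I − 0.125·11′), since 0.5/(1 + 6×0.5) = 0.125.

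- A = 2(380 − 0.125×40²) = 360
- B = 2(40 − 0.125×7×40) = 10
- C = 2(7 − 0.125×49) = 1.75
- RE = 1 − 100/(360×1.75) = 0.841, a variance cut of 15.9%

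If the planned test has 80% power, its standardized effect is 1.960 + 0.842 = 2.802. Under the common mean this becomes 2.802/√0.841 = 3.055, and power is Φ(3.055 − 1.960) = 86.3%.

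**Random intercept only, across the assumed range:**

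| Between SD | Within SD | ICC | Cut, Days 0–14 | 80% becomes | Cut, Days 0–28 | 80% becomes |
|---|---|---|---|---|---|---|
| 1.0 | 1.5 | 0.31 | 26.9% | 90.6% | 19.5% | 87.8% |
| 1.0 | 1.0 | 0.50 | 15.9% | 86.3% | 10.8% | 84.3% |
| 1.7 | 1.5 | 0.56 | 13.1% | 85.2% | 8.8% | 83.5% |
| 1.7 | 1.0 | 0.74 | 6.6% | 82.6% | 4.3% | 81.7% |

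At ICC 0.3 / 0.5 / 0.7 over Days 0–14, the constrained model matches the plan's 120 patients with about 87 / 101 / 110. At ICC 0.9 the gain is about one point of power (80% to 80.9%).

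**Random slope of SD 0.1 per day added to V.** The cut falls to 2.6–16.1% over Days 0–14 and 0.5–4.6% over Days 0–28.

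**Visit as a factor.** For a true difference that grows linearly over Days 0–14, the joint test moves from 80% to 92.3% / 87.4% / 83.8% at ICC 0.3 / 0.5 / 0.7. The gain therefore does not require a linear-time model.

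**Validity.** With 400,000 simulated trials and no treatment effect, both tests reject about 5% of the time overall. The planned armXtime estimate correlates with the chance Day-0 difference at −0.39 / −0.33 / −0.25 (ICC 0.3 / 0.5 / 0.7); under the common mean the correlation is 0. Among trials whose Day-0 difference exceeds +1 standard error, the planned test rejects 7.7% / 7.0% / 6.0% of the time and the constrained test about 5%.

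**The case against.** The strongest reply is that the planned model is a standard, valid analysis and that this is a preference about efficiency. The first half stands: type I error is held on average, and the case rests on precision alone.

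Four stronger readings are tempting, and the documents do not support them.

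- *The test is biased.* It is not. The raised rejection rate appears only conditional on an imbalance in one direction, and it averages out over randomizations.
- *A chance Day-0 difference passes whole into the result, as in a raw change from baseline.* If the Day-0 SD were 2 log10, the chance difference would have SD 2√(2/60) = 0.37 log10. But with a participant random effect and seven swabs the stable between-person part cancels. Only visit-level Day-0 noise enters, and correlations of −0.25 to −0.39 mean about 6–15% of the variance of armXtime.
- *That chance difference rivals the drug effect.* The documents give no viral-load effect size to compare it with.
- *The loss can be read from power at one visit, such as Day 7.* The SAP tests armXtime and plans no single-visit contrast for this model.

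Two further objections stand in part. The size depends on variances that nobody has stated, and it is small if the ICC is high or slopes vary widely. And under linear time, dropping the arm term needs more than randomization: it makes the arm difference proportional to time from Day 0. With slope SD 0.1 and an assumed effect starting after Day 5, one check gave 85.3% power for the constrained test against 86.5% for the planned one. This is why visit as a factor or flexible time is the better form.

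**Conclusion.** The concern holds as a matter of precision. SAP 2.4 spends information on a parameter that randomization makes zero in expectation, and no other provision recovers it. With linear time and the stated random intercept, a common Day-0 mean cuts the variance of armXtime by about 7–27% (Days 0–14) or 4–20% (Days 0–28), which turns 80% power into about 82–91%. With a random slope of SD 0.1 per day the cut is about 0.5–16%. All of this rests on assumed SDs, on the AUC swab days applying to this model, and on the Day-0 swab preceding the injection.

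The consequence is limited to a secondary endpoint and its exploratory nasal counterpart; the primary analysis is untouched. The change is worth making because it is nearly free.

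**What to change.** Before unblinding, amend SAP 2.4 to state that:

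- the Day-0 oropharyngeal swab is a response in the model, after confirming and recording that it is taken before the injection;
- both arms share a common Day-0 mean, preferably with visit as a factor (visit plus arm-by-post-baseline-visit terms, no arm term at Day 0) or with flexible time constrained in the same way;
- the arm comparison is a joint test of the post-baseline arm terms, with age and sex retained;
- if linear time is kept, omitting the arm main effect assumes a difference that grows in proportion to time, which can slightly reduce power for a delayed effect.

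Apply the same form to the nasal model in SAP 2.5. The cost is a short SAP amendment and a check of swab timing, with no new data or visits. Fixing the form now also prevents a choice made after the baseline imbalance is known.
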